	
System in a post-market (commercial device use) setting will be enrolled and will be followed for 24 months post index procedure.
 
Enrolled subjects will undergo endovascular PAD treatment that includes atherectomy using the AURYON system, according to institutional standard of care. Data collection will include prospective data collection and medical record review of procedures performed according to standard of care, at the study protocol specific follow up time-points.

OBJECTIVES:	To evaluate the safety and efficacy of AURYON Atherectomy System in the treatment of de novo, re-stenotic and ISR lesions in infra-inguinal arteries of Peripheral Artery Diseases (PAD) subjects, in a real-world setting. This is a pilot registry study towards a subsequent large pivotal registry (PATHFINDER II).
ENDPOINTS:	
Primary Endpoints:
 
 1. Primary Efficacy: Acute Procedural Success Percentage of subjects with successful revascularization of target vessel defined as $\leq 30\%$ residual stenosis at the index lesion post atherectomy using the AURYON system and final adjunctive treatment (if required), as evaluated by angiographic corelab. 2. Primary Safety: Percentage of subjects with freedom from peri-procedural major adverse events (PPMAE), defined as (a) flow-limiting dissection, (b) clinically significant distal embolization, (c) bailout stenting, (d) major/unplanned amputation, (e) target vessel perforation requiring endovascular or surgical repair or (f) death, till discharge. 
Secondary endpoint(s):
 
 1. Rate of device related complications requiring intervention, defined as peri procedural MAEs, reported by the operating physician as caused directly due to the use of the AURYON device. 2. Rates of post-discharge MAEs over time; defined as: (a) Unplanned target limb amputation, (b) cardiovascular death, (c) clinically driven target lesion revascularization¹, (d) target vessel revascularization (TVR). 3. Patency rate, defined as (1) $< 50\%$ stenosis at the treated lesion, with peak systolic velocity ratio (PSVR) of < 2.5, as

[figure not shown]
¹ Clinically-Driven Target Lesion Revascularization (CD-TLR), defined as a reintervention performed for $\geq 50\%$ diameter stenosis (confirmed by angiography) within 5 mm of the target lesion after documentation of recurrent clinical symptoms of PAD following the index procedure.

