	
assessed quantitatively by Duplex ultrasonography (DUS); OR, (2) for BTK lesions: freedom from occlusion (100% stenosis by DUS) combined with freedom from CD-TLR, at 6, 12, and 24 months.
 
4. Clinical outcomes, defined as change in ankle brachial index (ABI or TBI if needed), walking impairment questionnaire (WIQ), and Rutherford category at 6, 12, and 24, months, compared to baseline
 
Exploratory endpoint(s):
 
1. Intravascular ultrasound assessment pre- and post-Auryon and correlation with angiographic findings (e.g. lesion length, MLA -minimal lumen area gain, calcium severity and removal, etc.). This endpoint will be analyzed only for cases that used IVUS as a routine practice in the index procedure.

STUDY POPULATION:	
Patients with infra-inguinal PAD undergoing atherectomy with the AURYON Atherectomy System.
 
Inclusion Criteria A potential subject will be included in the study if he/she meets all the following inclusion criteria:
 
 1. Subject is ≥ 18 years old. 2. Subject is a candidate for atherectomy for infra-inguinal peripheral artery disease. 3. Documented symptomatic atherosclerotic peripheral artery disease with claudication or critical limb ischemia (CLI) (Rutherford Classification 2-5). 4. Subject is capable and willing to comply with the scheduled follow up 5. Subject is able and willing to sign a written Informed Consent Form (ICF). 
Exclusion Criteria A potential subject will be excluded from the study if he/she meets any of the following exclusion criteria:
 
 1. Target lesion is in an arterial bypass. 2. Planned use of another atherectomy device in the same procedure 3. Co-morbid condition(s) with less than 1yr anticipated survival that could limit the subject's ability to participate in the trial or to comply with follow-up requirements or impact the scientific integrity of the study.

	4. Participating in another study on an interventional non-cleared device, that could impact the study results

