DESCRIPTION OF SITES/FACILITIES ENROLLING PARTICIPANTS:	
This study will be conducted at sites where eligible PAD patients are routinely treated with atherectomy by AURYON Atherectomy System.
 
Total enrollment of approximately 100 subjects at approximately 10 sites in the US.
 
To reduce bias by sites, each site may enroll up to 15 eligible subjects whom have successfully completed their index atherectomy treatment with the AURYON system and with analyzable imaging for the primary efficacy analysis.

DESCRIPTION OF STUDY PROCEDURE:	Atherectomy by the AURYON system, of infra-inguinal stenoses, occlusions or in-stent restenosis (ISR).
STUDY DURATION:	The study duration is expected to be two and a half (2.5) years: 6 months to enroll and two (2) years to follow up all subjects.
PARTICIPANT DURATION:	Two (2) years
PRIMARY ANALYSIS PLAN:	
As this is a pilot registry study, no formal hypotheses are defined; rather statistical analyses will be descriptive in nature and will serve to provide estimates of the primary and secondary study endpoints.
 
Also, no formal sample size calculation was performed. The number of enrolled subjects will allow for sufficient safety monitoring and evaluation of the safety and efficacy endpoints and will provide point estimates for the large-scale registry.
 
Analysis sets:
 
Intent-to-treat (ITT) population: The intent-to-treat (ITT) population will consist of all subjects who signed the informed consent form and underwent procedure with an attempt of using the AURYON system.
 
Modified Intent-to-treat (mITT) population: The modified Intent-to-treat (mITT) population will consist of all ITT subjects who underwent atherectomy using the AURYON system for at least one lesion.
 
Per-protocol (PP) population

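### Secondary endpoint 3 requires freedom from CD-TLR only in its BTK rule, so a non-BTK lesion that was re-treated and is open at the visit is scored patent

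*Combined protocol and SAP*

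**What the plan says.** All of this is in section 2 (Protocol Summary) unless noted.

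- **Rule (1)** of secondary endpoint 3 requires less than 50% "stenosis at the treated lesion, with peak systolic velocity ratio (PSVR) of < 2.5, as" measured by duplex. It names no lesion site and sets no condition on reintervention.
- **Rule (2)** follows a semicolon and the word OR: "assessed quantitatively by Duplex ultrasonography (DUS); OR, (2) for BTK lesions: freedom from occlusion (100% stenosis by DUS) combined with freedom from CD-TLR". Patency is assessed at 6, 12 and 24 months.
- **CD-TLR** is defined in a footnote as a reintervention for a stenosis of at least 50%, confirmed by angiography, "within 5 mm of the target lesion after documentation of recurrent clinical symptoms of PAD following the index procedure".
- **CD-TLR is also counted** under secondary endpoint 2 as a component of post-discharge MAEs: "c) clinically driven target lesion revascularization".
- **The population** covers all infra-inguinal disease, so both BTK and non-BTK lesions are expected.
- **The analysis** is descriptive ("Also, no formal sample size calculation was performed"), but it is meant to supply point estimates for the larger registry.

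In the text available, nothing says that a lesion with a prior CD-TLR is a patency failure or is censored. The rate is not labelled as primary, assisted or secondary patency.

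**The concern.** Rule (1) is a snapshot: it looks only at the scan on the visit date. Section 4, Table 1 schedules duplex at 6, 12 and 24 months. A non-BTK lesion that fails and is repaired at month 8 can look open at month 12, and the result of the second procedure is then credited to the index treatment.

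The protocol's own footnote makes such a lesion hard to regard as patent throughout. CD-TLR requires a symptomatic stenosis of at least 50% at or within 5 mm of the lesion, whereas rule (1) requires less than 50%. The measurement differs (angiography against duplex), but the event lies on the failing side of the same threshold. Rule (2) does treat CD-TLR as failure, and no reason is given for treating other lesions differently.

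At stake is the meaning of the only imaging-based durability endpoint. A pooled rate would combine one group in which re-treatment is a failure with another in which it is not, and would pass into planning for a registry of about 1000 patients.

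**Working it through.** The plan states no patency rate, CD-TLR rate or lesion mix, so there is no figure to reproduce. The check has two parts.

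**1. Truth table.** Each lesion type is scored under three rules: the literal OR; OR read as a split by site (rule 1 for non-BTK, rule 2 for BTK); and a split by site with freedom from CD-TLR required in both. The scan states are illustrative: open (20%, PSVR 1.2), restenosed (70%, PSVR 4.0) and occluded (100%).

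| Lesion | Prior CD-TLR | Scan | Literal OR | Split by site | CD-TLR-free in both |
|---|---|---|---|---|---|
| non-BTK | no | open | patent | patent | patent |
| non-BTK | no | restenosed | not | not | not |
| **non-BTK** | **yes** | **open** | **patent** | **patent** | **not** |
| non-BTK | yes | restenosed | not | not | not |
| BTK | no | open | patent | patent | patent |
| BTK | no | restenosed | patent | patent | patent |
| **BTK** | **yes** | **open** | **patent** | **not** | **not** |
| BTK | yes | restenosed | not | not | not |
| either | either | occluded | not | not | not |

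Three things follow.

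- The non-BTK result does not depend on how OR is read.
- The BTK result does: the lesion passes only through rule (1) under the literal OR.
- Every change between the current text and the last column is from patent to not patent, so the current wording can only raise the rate.

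The table also shows the two thresholds. Without CD-TLR, a 70% stenosis is patent if BTK and not patent otherwise, so a pooled rate moves with the lesion mix.

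**2. Size.** Let *s* be the share of lesions affected, *t* the proportion with CD-TLR by the visit, and *u* the share of re-treated lesions open at the visit.

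Overstatement in percentage points = 100 × *s* × *t* × *u*

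Under the split by site, *s* is the non-BTK share; under the literal OR, *s* = 1. The formula takes *t* and *u* as equal across sites and assumes every lesion is scanned. All inputs are assumptions: non-BTK share 0.5-0.9, *t* 0.05-0.20, *u* 0.5-1.0.

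| Case | Split by site | Literal OR |
|---|---|---|
| Lowest | 100 × 0.5 × 0.05 × 0.5 = 1.25 | 100 × 1 × 0.05 × 0.5 = 2.5 |
| Example (0.7 non-BTK, *t* 0.10, *u* 0.8) | 100 × 0.7 × 0.10 × 0.8 = 5.6 | 100 × 1 × 0.10 × 0.8 = 8.0 |
| Highest | 100 × 0.9 × 0.20 × 1.0 = 18 | 100 × 1 × 0.20 × 1.0 = 20 |

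**The case against.** The case for leaving the text alone has four parts.

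- **Role of the endpoint.** Patency is the third secondary endpoint of an unpowered pilot with no formal hypotheses. No primary result, test or sample size rests on it. This stands and limits the severity. It does not remove the point, because providing estimates is the study's stated purpose.
- **Re-treatments are visible elsewhere.** CD-TLR and TVR are reported under endpoint 2(c) and 2(d). This also stands. A reader might infer that the plan conceals failures; it does not. The misclassification lies within the patency rate, and the separate CD-TLR figure does not correct that rate.
- **Openness irrespective of reintervention is a coherent quantity,** and the plan never says primary patency. That would be an answer if the rate were labelled so and both rules followed it. Rule (2) does not.
- **Site-specific criteria are deliberate.** They are explicit in the text, and nothing rules out separate presentation. Different thresholds are therefore not an error in themselves; the concern is only a pooled rate shown alone.

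A reader might also infer that re-treated BTK lesions are certainly scored patent. The documents do not settle that: the words introducing rule (2) read naturally as a split by site, under which those lesions already fail. A reading that carries the CD-TLR condition back to rule (1) is possible, but the numbering and semicolon work against it.

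**Conclusion.** The point holds for non-BTK lesions on any natural reading: a re-treated, re-opened lesion is scored patent. For BTK lesions it holds only under the literal OR. The direction is certain, and the size is not. The overstatement is about 1 to 18 points split by site, or 2.5 to 20 points under the literal OR, and both ranges rest wholly on assumed lesion mix, CD-TLR and re-opening rates.

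Two stronger conclusions are not supported. The documents contain nothing that would fix a particular inflation within those ranges, and a figure that leaves out lesion mix would hold only if every lesion were affected. Nor can the overstatement be said to grow steadily with follow-up: cumulative CD-TLR can only rise, but the share of re-treated lesions still open may fall.

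This is a should-fix, to be settled before patency is analysed or carried into the larger registry.

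**What to change.** Reword secondary endpoint 3 as follows.

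- Apply rule (1) to non-BTK lesions only and rule (2) to BTK lesions only. Non-BTK is safer than above-knee, which could leave a popliteal lesion at knee level under neither rule.
- In both rules, require freedom from CD-TLR of that lesion since the index procedure. Keep this at lesion level, as the definition is.
- Count a lesion with a prior CD-TLR as not patent at all later visits, including when the visit duplex is missing.
- Show the non-BTK and BTK rates separately beside any pooled rate, because their thresholds differ.
- If duplex openness irrespective of reintervention is of interest, show it as an additional result under that label.

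The cost is endpoint wording and programming. CD-TLR is already collected as an MAE, and note 4 to Table 1 provides for telephone contact when a visit is missed, so known cases can be classified without a scan. Where a subject has several treated lesions, the record must identify which one was re-treated; the text available does not show whether it does. The downside for the sponsor is a lower reported patency rate.

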2 PROTOCOL SUMMARY

TITLE:	PATHFINDER I: Post-Market Registry of Auryon Atherectomy Device in Subjects Affected with Infrainguinal Peripheral Artery Disease (PATHFINDER-Registry, EX-PAD-05)
DEVICE DESCRIPTION:	
The AURYON System consists of two sub-units: 1) a single use catheter ("AURYON catheter"); and 2) a laser system.
 
The AURYON catheter is a single use catheter that is made of an array of optic fibers and surrounded by a circumferential blunt blade at its distal tip. The AURYON catheter is connected to the laser system via its connector and transmits energy at pre-set fluence levels of 50 and 60 mJ/mm² to the occluded or narrowed artery. The AURYON System must work over a commercially available 300cm 0.014" guide wire (GW) that crosses the lesion intraluminally. - For the small size catheters (i.e., 0.9mm and 1.5mm), there is a designated lumen tube for a guidewire at the center of the inner blunt blade. Please note that 0.9mm and 1.5mm catheters do not have an aspiration feature and have not been tested in ISR lesions. These devices should not be used in ISR cases. The larger AURYON catheters (i.e., 2.0mm and 2.35mm) have an eccentric guidewire lumen, and include additional features consisting of an aspiration feature (both catheters) and an "off-center" feature (2.35mm only). The aspiration feature is intended for debris and thrombus collection and removal from the vessel during the atherectomy procedure. The "off-center" feature is included in the 2.35 mm catheter only and is designed to facilitate debulking of lesions in blood vessels beyond the catheter's diameter.

INDICATION FOR USE:	The AURYON system is indicated for use in the treatment, including atherectomy, of infra-inguinal stenoses and occlusions, including in-stent restenosis (ISR).
REGULATORY STATUS:	The device is cleared for sale in the US (K181642).
STUDY DESCRIPTION:	The PATHFINDER I Registry is a prospective, non-randomized, single arm, multicenter observational study. It is a pilot registry study towards a subsequent large pivotal phase registry. This pilot registry is aimed to evaluate the performance (peri-procedural) and clinical outcomes (intermediate and long-term) of the AURYON Atherectomy System, within the initial launch phase of the product in the market. After signing an informed consent form, eligible PAD subjects treated with the AURYON Atherectomy

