	
The per-protocol (PP) population will consist of all mITT subjects for whom the AURYON catheter fully crossed at least one target lesion.
 
If a subject does not undergo complete procedure, either due to early or intraoperative non-eligibility of inclusion/exclusion criteria or due to missing evidence of significant arterial disease ($\geq 50\%$) by fluoroscopy angiogram in the index procedure, the subject will be considered as a screen failure. Screen failures will not be included into ITT population and will not be followed or part of the analysis.
 
If a subject undergoes an atherectomy attempt but the AURYON system could not be successfully used in any target lesion, the subject will be included into ITT population but excluded from mITT and PP populations. That subject will not be followed-up after discharge.
 
If a subject undergoes atherectomy using the AURYON system but the AURYON catheter cannot fully cross the target lesion, the subject will be included into ITT and mITT populations but excluded from PP population. That subject will be followed-up after discharge at 30-day, 6-month, 12-month and 24-month visits.
 
Analyses of all primary & secondary endpoints will be conducted in both the mITT and PP populations. The ITT population will serve as the primary set for safety assessments.

RATIONALE FOR NUMBER OF PATIENTS:	
With a total of 100 patients successfully treated by AURYON system in this study cohort, this study will serve as an unpowered pilot registry, towards a larger powered registry study that is planned to include approximately 1000 patients.

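### Change in ABI/TBI, WIQ and Rutherford at 6 to 24 months has no stated link to reintervention, amputation or death, so re-treated subjects can be reported as improved

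*Combined protocol and SAP*

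**What the plan says.** All of the following is in section 2 (Protocol Summary) unless another section is named.

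- **Endpoint.** Secondary endpoint 4 is "Clinical outcomes, defined as change in ankle brachial index (ABI or TBI if needed), walking impairment questionnaire (WIQ), and Rutherford category", taken "at 6, 12, and 24, months, compared to baseline". No condition is attached.
- **Events expected after discharge.** Secondary endpoint 2 counts "a) Unplanned target limb amputation, (b) cardiovascular death, (c) clinically driven target lesion revascularization" and, as item (d), TVR. Footnote 1 makes documented recurrence of PAD symptoms part of the definition of CD-TLR.
- **Where reintervention is handled.** The below-the-knee part of the patency endpoint requires "freedom from occlusion (100% stenosis by DUS) combined with freedom from CD-TLR, at 6, 12, and 24 months". Endpoint 4 has no equivalent.
- **Analysis sets.** "Analyses of all primary & secondary endpoints will be conducted in both the mITT and PP populations". Membership of either set depends only on what happened at the index procedure.
- **Follow-up.** Subjects "will be followed for 24 months post index procedure". Table 1 (section 4) schedules ABI, Rutherford and WIQ at 6, 12 and 24 months, with no exception after a repeat procedure or amputation. The telephone fallback for a missed visit names adverse events and medications, not these three measures.
- **Purpose.** The study description says that the registry evaluates "clinical outcomes (intermediate and long-term) of the AURYON Atherectomy System". The primary analysis plan adds that the analyses are descriptive and will supply point estimates for the larger registry.

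**The concern.** The plan expects some index treatments to fail within 24 months and counts those failures in one endpoint. It then measures clinical status in another endpoint without connecting the two. Two things follow.

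1. A subject whose symptoms return and who is re-treated before a visit contributes the ABI, WIQ and Rutherford category that follow the second procedure. The same person can be a CD-TLR in endpoint 2 and an improvement in endpoint 4.
2. ABI or TBI cannot be taken on a limb lost to major amputation, and nothing can be measured in a subject who has died. These outcomes leave the ABI/TBI mean and do not lower it.

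With one arm, no comparison group carries the same effect. A 12- or 24-month change would naturally be read as durability of the index treatment, although part of it may come from later procedures and from loss of the worst outcomes. The same reading would pass into the larger registry.

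**Working it through.** **Step 1: is there a rule?** The documents give no figure for endpoint 4, so there is nothing to reproduce. The check is a reading of the places listed above. Endpoint 4 is unconditioned, the analysis sets ignore events after the index procedure, Table 1 makes no exception, and the only outcome at 6 to 24 months that takes account of reintervention is below-the-knee patency. The text reviewed sets no rule for reintervention, amputation, death or missing values in endpoint 4.

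**Step 2: which measures lose amputees?**

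| Measure | After major target limb amputation |
|---|---|
| ABI/TBI | Cannot be taken on that limb |
| WIQ | Completed by the subject, so still obtainable |
| Rutherford | Might still be assigned; the documents do not say |

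**Step 3: ceiling from re-treatment alone.** Let f be the share of subjects measured at a visit who were re-treated before it. At most all of them are classed as improved, so they make up at most 100 × f points of the improved rate. With f assumed to be 10–25%, the ceiling is 10–25 points. If 75% of them are classed as improved (also assumed), the contribution is 0.75 × 10 = 7.5 to 0.75 × 25 = 18.75 points.

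**Step 4: gap between the two definitions.** This is an illustration and every rate is assumed. Take 75% improved among those measured, re-treated or not; reintervention r = 10, 20 or 30%; amputation a = 2–5%; death d = 5–10%; events not overlapping; amputees and deaths absent from the measured group.

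- As written: 75%.
- All three events scored as not improved: 0.75 × (1 − r − a − d).
- The same with deaths left out of the denominator: 0.75 × (1 − r − a − d) / (1 − d).

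Lowest assumed rates: 0.75 × (1 − 0.10 − 0.02 − 0.05) = 0.75 × 0.83 = 62.25%, or 62.25 / 0.95 = 65.5% without deaths. Highest assumed rates: 0.75 × (1 − 0.30 − 0.05 − 0.10) = 0.75 × 0.55 = 41.25%, or 41.25 / 0.90 = 45.8% without deaths.

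| r | Deaths not improved | Gap from 75% (points) | Deaths left out | Gap from 75% (points) |
|---|---|---|---|---|
| 10% | 56.25–62.25% | 12.75–18.75 | 62.5–65.5% | 9.5–12.5 |
| 20% | 48.75–54.75% | 20.25–26.25 | 54.2–57.6% | 17.4–20.8 |
| 30% | 41.25–47.25% | 27.75–33.75 | 45.8–49.7% | 25.3–29.2 |

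With deaths scored as not improved, the gap is 0.75 × (r + a + d). Amputation therefore contributes only 0.75 × 2 = 1.5 to 0.75 × 5 = 3.75 points, and the uncertainty about recording Rutherford after amputation changes little.

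**Step 5: comparison with sampling error.** At n = 100 and 75%, the 95% half-width is 1.96 × √(0.75 × 0.25 / 100) = 0.085, or 8.5 points. Under these assumptions the choice of rule moves the result by more than sampling error does.

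**The case against.** The strongest reply is that status at each visit, whatever care came in between, is a legitimate descriptive target in a real-world registry. Reinterventions, amputations and cardiovascular deaths are reported in endpoint 2, so readers see the failures in the same report. The endpoint is also secondary, in an unpowered pilot with no hypotheses. All of that stands. It is the reason to keep the planned change from baseline and not to replace it. It does not remove the gap: two separate tables do not show how many of the improved subjects were re-treated, and a descriptive estimate still needs a defined quantity.

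Three further points stand:

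- The text reviewed stops at the schedule of activities in section 4, so a later detailed section could contain a rule.
- No size can be taken from the documents; the rates above are all assumed.
- Splitting ABI or WIQ by prior revascularization is not a clean remedy. It conditions on something that happened after the index procedure, and the group without revascularization is selected for success.

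A reader might infer that the plan directs these measures to be taken regardless of later events. It does not; it sets no rule, and an unconditioned change at fixed visits has that effect. A reader might also infer that amputees vanish from all three measures. That is firm only for ABI/TBI. Nor do the documents support the inference that mean changes must rise as more failures are re-treated: a re-treated subject may only regain, or fall short of, the earlier gain.

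**Conclusion.** The concern holds in limited form. Endpoint 4 as written allows a documented symptomatic recurrence to be reported as improved after a second procedure, and it leaves limbs lost to major amputation and subjects who died out of the ABI/TBI mean. This can overstate how long the benefit of the index treatment lasts, which is part of the registry's stated aim.

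The size is unknown. If 10–25% of measured subjects had been re-treated, up to 10–25 points of an improved rate could be re-treated subjects. The wider illustration gives a gap of about 13–34 points between the two definitions, or about 10–29 points with deaths left out of the denominator. It rests on an assumed 75% improved, 10–30% reintervention, 2–5% amputation and 5–10% death. None of these comes from the plan, which does not define an improved rate either.

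The change is worth making but not critical, because the endpoint is secondary and descriptive. It matters mainly because the estimates are meant to inform the larger registry.

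**What to change.** 1. Keep change from baseline in ABI/TBI, WIQ and Rutherford, and say that it describes status at each visit, including the effect of any later procedure.
2. Add sustained clinical improvement at 6, 12 and 24 months: at least one Rutherford category better than baseline, with no CD-TLR, TVR or unplanned target limb amputation since the index procedure. Score a subject with any of these events as not improved.
3. Score cardiovascular death as not improved, and show a second version with deaths left out of the denominator. Say how other deaths are treated, since endpoint 2 names only cardiovascular death.
4. Beside each ABI/TBI, WIQ and Rutherford summary, give the numbers with prior CD-TLR or TVR, with amputation, dead, and with missing values.
5. If ABI or WIQ is split by prior revascularization, label the split as descriptive, because it conditions on an outcome after the index procedure.

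**Cost.** Wording, one added analysis and extra table columns; no new visits or subjects. The definition uses only events that endpoint 2 already lists. Extending it to any target limb revascularization, or to planned major amputation, would go beyond that list and might require changes to the data collection forms. The downsides are slightly more analysis and a long-term improvement rate that looks lower.

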3 STUDY SCHEMA

4 SCHEDULE OF ACTIVITIES

Table 1. Schedule of Events for Screening and Enrollment, AURYON atherectomy Procedure and Post-Procedure Follow-up

Study assessment	Pre-Procedure	Procedure	Post-procedure	Hospital discharge	30 Days (±1 weeks)	6, 12, 24 Months (±1 Month)
Medical history & demographics	X					
Physical Examination	X					X
Informed Consent	X					
Angiographic evaluation of target lesion	X	X	X			
PAD Intervention including AURYON Atherectomy		X				
Quantitative DUS						X
ABI ⁰	X					X
Rutherford Classification	X					X
WIQ	X					X
Record of relevant medications ¹	X	X		X	X ³	X ⁴
Record of PPMAEs ² and other procedural complication		X	X	X		
Record of MAEs ²					X ³	X ⁴

⁰ Toe-brachial index (TBI) will be taken for subjects with non-compressible vessels

¹ Relevant medications: anticoagulant and anti-platelets.

² Adverse events should only be captured after signing of the Informed Consent Form.

³ The visits may be done via phone call for record of any reportable adverse events and relevant medications.

⁴ In case that subject is not showing up to one or more of these follow-up visits, the site should contact the subjects by telephone to collect as much data as possible of any reportable adverse events and relevant medications.

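### The exploratory IVUS endpoint names only correlation with angiography; for measures both methods take on one scale, agreement should be reported as well, on images from the same step of the procedure

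*Combined protocol and SAP*

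**What the plan says.** Section 2 (Protocol Summary, exploratory endpoint 1) sets the endpoint as "Intravascular ultrasound assessment pre- and post-Auryon and correlation with angiographic findings". Its examples are "lesion length, MLA -minimal lumen area gain, calcium severity and removal, etc". The subset is restricted: "This endpoint will be analyzed only for cases that used IVUS as a routine practice in the index procedure". No coefficient, measure of agreement, paired time point or IVUS reader is given there.

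Three other places bear on which angiogram would be used:

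- The primary efficacy endpoint (Section 2) assigns one reading to the core laboratory: residual stenosis "post atherectomy using the AURYON system and final adjunctive treatment (if required), as evaluated by angiographic corelab".
- Table 1 (Section 4) has a row "Angiographic evaluation of target lesion", marked at Pre-Procedure, Procedure and Post-procedure. It names no reader and does not divide the procedure into before and after adjunctive treatment. The table has no IVUS row.
- The screen-failure rule (Section 2, analysis sets) requires significant disease "by fluoroscopy angiogram in the index procedure", with no core laboratory mentioned.

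On size, Section 2 gives "Total enrollment of approximately 100 subjects at approximately 10 sites in the US" and states that "no formal sample size calculation was performed". The number of IVUS cases is not stated.

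**The concern.** Lesion length and calcium severity can be read by both IVUS and angiography. For such pairs the natural question is how far apart the two readings are. Correlation does not answer it. Adding a constant to one method, or multiplying it by a constant, leaves the correlation of the underlying values unchanged. With measurement error held fixed, the coefficient also moves with the range of lesions enrolled. A high value can therefore accompany a large systematic difference, and a low value may only reflect a narrow case mix.

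A separate question is timing. IVUS is tied to the state of the vessel after AURYON, while the one core-laboratory result defined is tied to the end of the procedure. If those two were paired in a subject who had adjunctive treatment, the effect of that treatment would appear as a difference between imaging methods.

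The pilot is meant to prepare a registry of about 1000 patients. A coefficient that cannot be interpreted is a poor guide to which imaging measure to carry forward.

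**Working it through.** The documents give no correlation, agreement target or IVUS count, so there is no planned figure to reproduce. Every mean, SD and bias below is an assumption chosen to show how the statistics behave.

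**1. Proportional difference in lesion length.** Let angiographic length X be log-normal with median 80 mm and log-SD 0.6, and IVUS Y = 1.3X + error, error SD 10 mm.

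- Mean of X = 80 × exp(0.6²/2) = 95.8 mm. Variance = 95.8² × (exp(0.36) − 1) ≈ 3975, so SD = 63.1 mm.
- r = 1.3 × 63.1 / √(1.69 × 3975 + 100) = 82.0 / 82.6 = 0.993.
- Mean difference = 0.3 × 95.8 = 28.7 mm.
- SD of the difference = √(0.09 × 3975 + 100) = 21.4 mm. 95% limits = 28.7 ± 1.96 × 21.4, about −13 to +71 mm.
- Lin's concordance coefficient = 2 × 1.3 × 3975 / (3975 + 6818 + 28.7²) = 0.89.

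**2. A range of systematic differences.** Simulation of 200,000 pairs; length normal with mean 80 and SD 40 mm, floored at 20 mm; reading noise SD 4 mm.

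| IVUS relative to angiography | r | Concordance | Mean difference (mm) | Pairs within 10% |
|---|---|---|---|---|
| same | 0.994 | 0.994 | 0.0 | 86.5% |
| × 1.2 | 0.996 | 0.910 | 16.2 | 6.0% |
| × 1.5 | 0.998 | 0.678 | 40.5 | 0.2% |
| + 20 mm | 0.994 | 0.872 | 20.0 | 1.7% |
| + 40 mm | 0.994 | 0.637 | 40.0 | 0.0% |

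The correlation barely moves, while the share of close pairs collapses.

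**3. Dependence on spread.** Let Y = X + error with SD 20 mm and no bias. The limits are ±1.96 × 20 = ±39 mm in every case, and r = √(Var X / (Var X + 400)).

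- Log-SD 0.2: Var X = 272, r = 0.64.
- Log-SD 0.4: Var X = 1303, r = 0.875.
- Log-SD 0.6: Var X = 3975, r = 0.95.

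The error is identical; only the case mix differs.

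**4. Calcium grade.** Take 10 lesions each at angiographic grades 0, 1 and 2, with IVUS one grade higher throughout. Spearman is 1.00 and exact agreement 0%. Chance agreement is 1/9 + 1/9 = 2/9, so unweighted kappa = (0 − 2/9)/(1 − 2/9) = −0.29. Weighted kappa is 1 minus observed over expected disagreement. With linear weights it is 1 − 1/(11/9) = 0.18; with quadratic weights, 1 − 1/(21/9) = 0.57. The weights therefore matter, and exact agreement belongs beside kappa.

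**5. Mixed stages.** Suppose two error-free methods on a common percent-stenosis scale, post-AURYON stenosis of mean 45 and SD 15, and adjunctive treatment lowering it by m points.

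- With a constant drop, r = 1.00, the apparent bias is −m, and concordance = 2 × 225/(450 + m²): 0.82, 0.53 and 0.33 for m = 10, 20 and 30.
- If the drop varies with SD s, r = 15/√(225 + s²): 0.95, 0.83 and 0.71 for s = 5, 10 and 15.

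None of this is a difference between methods.

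**6. Precision.** By Fisher's z, with half-width 1.96/√(n − 3), an observed r of 0.90 has a 95% interval of 0.62–0.98 at n = 10, 0.80–0.95 at n = 30 and 0.85–0.93 at n = 100. The last is about the most that the planned enrolment allows at one pair per subject.

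**The case against.** The plan nowhere claims that the two methods are interchangeable, and correlation may be meant loosely as a description of how they relate. For unlike quantities, such as IVUS lumen area against angiographic percent stenosis, correlation is a reasonable summary and limits of agreement do not apply. Converting an angiographic diameter to an area assumes a round lumen and could itself create disagreement. This stands, and it confines the point to like-for-like measures.

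On timing, a reader might infer that post-AURYON IVUS will be set against the final core-laboratory reading. The documents do not support that. The endpoint refers to angiographic findings without naming the core laboratory or the final image, and Table 1 schedules angiography before, during and after the procedure, so a same-step image may exist. Comparisons made before AURYON, and subjects with no adjunctive treatment, are unaffected. What remains is narrower: the sections reviewed neither separate post-AURYON from post-adjunctive angiography nor name a reader for these images.

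A reader might also infer that a near-perfect correlation would conceal complete disagreement. The 30% length example does not show that, since its concordance is 0.89. The calcium example reaches 0% agreement only because every lesion is shifted one grade, which is impossible for a lesion already in the top grade by angiography.

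Finally, fixed limits fit a proportional difference poorly. At 80 mm the model in step 1 implies 24 ± 1.96 × 10, about +4 to +44 mm, against overall limits of −13 to +71 mm. This also stands and shapes the fix.

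**Conclusion.** The point holds for lesion length, and for calcium grade where both methods grade it: the one comparison named cannot show whether the readings agree. That is a property of correlation and does not rest on the assumed inputs; only the illustrated sizes do. No passage indicates how large any real IVUS–angiography difference will be.

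The stage question is a gap in specification, not a demonstrated mismatch. Nor is a scale conflict established for the primary result: the protocol calls it residual stenosis, and the term diameter stenosis appears only in the footnote on clinically driven revascularization.

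The importance is minor. The endpoint is exploratory, in an unpowered descriptive pilot without hypotheses, and no primary or secondary conclusion depends on it. The descriptive aim is no reason to leave agreement out, since a mean difference and its limits are themselves descriptive.

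**What to change.** Amend the analysis text for exploratory endpoint 1:

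- Keep correlation for unlike quantities.
- For lesion length and any other measure on a common scale, report beside it the mean difference with 95% limits of agreement, on the log or ratio scale if the difference grows with size.
- For calcium grade, where both methods grade it, report weighted kappa with the weights named in advance, plus exact agreement.
- Give confidence intervals and the number of pairs for each.
- Pair each IVUS run with an existing angiogram from the same step, and state who reads each image. Where adjunctive treatment was given and no reading from before it exists, do not pair post-AURYON IVUS with the final core-laboratory result. Report how many pairs are lost.

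The cost is a few extra tables and fewer post-AURYON pairs, in a subset already limited to routine IVUS users; the remaining pairs may be selected. The documents do not show that angiograms from before adjunctive treatment, or angiographic calcium grades, are read. New core-laboratory readings would be an added expense, and this fix does not require them.
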